8.4 Partial Remission (PR)

For patients to be classified as being in PR, they must have bone marrow regenerating normal hematopoietic cells with evidence of peripheral recovery with no (or only a few regenerating) circulating blasts and with a decrease of at least 50% in the percentage of blasts in the bone marrow aspirate with the total marrow blasts between 5% and 25% and meet the criteria for CR.

8.5 Morphologic leukemia-free state:

≤

8.6 Hematologic Improvement (HI): Hematologic response must be described by the number of positively affected cell lines.

- ◆ **Erythroid response (E)** (pretreatment Hgb <11 g/dL)
Hgb increase by ≥ 1.5 g/dL
- ◆ **Platelet response (P)** (pretreatment platelets <100 $\times 10^9$ /L)
Absolute increase of $\geq 30 \times 10^9$ /L for patients starting with $> 20 \times 10^9$ /L platelets
Increase from $< 20 \times 10^9$ /L to $> 20 \times 10^9$ /L and by at least 100%
- ◆ **Neutrophil response (N)** (pretreatment ANC <1.0 $\times 10^9$ /L)
At least 100% increase and an absolute increase $> 0.5 \times 10^9$ /L
- ◆ **Blast response (B)**
 $\geq 50\%$ reduction in bone marrow blasts but still $> 5\%$

8.7 Recurrence of Disease

Relapse after CR is defined as a reappearance of leukemic blasts in the peripheral blood or $\geq 5\%$ blasts in the bone marrow aspirate not attributable to any other cause or reappearance or new appearance of extramedullary leukemia. Relapse after PR is similarly defined with reappearance of significant numbers of peripheral blasts and an increase in the percentage of blasts in the bone marrow aspirate to $> 25\%$ not attributable to any other cause or reappearance or new appearance of extramedullary leukemia.

8.8 Best Response measurement

Response will be measured and defined for primary endpoints as the best response achieved during the first 3 cycles of therapy, or at time off study, for those patients discontinuing treatment before the completion of 3 cycles of therapy. Best response is defined to be the best-measured response (CRc=CR+CRp+CRi, PR, or marrow clearance) post-treatment up to that time. Best response will also be evaluated for the full treatment period using all assessments up to and including treatment discontinuation.

9.0 DISCONTINUATION OF TREATMENT:

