1.0 OBJECTIVES

1.1 Primary Objectives

Phase Ib

1. To determine the maximum tolerated dose (MTD) and the recommended phase 2 dose (RP2D) of the combination of venetoclax with quizartinib in FLT3-ITD mutated patients with relapsed/refractory acute myeloid leukemia (AML).

Phase II

1. To determine the composite CR (CRc) rate including CR (complete remission) + CRp (complete remission with incomplete platelet recovery) + CRI (complete remission with incomplete count recovery) within 3 months of treatment initiation in FLT3-ITD mutated patients with relapsed/refractory AML.

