2.4 RATIONALE FOR STUDY

Second generation FLT3 inhibitors such as quizartinib and gilteritinib demonstrate potent anti-leukemic activity and improve outcomes in patients with relapsed/refractory AML with *FLT3-ITD* mutations(22). About 40-55% of FLT3-mutated patients not previously exposed to FLT3-inhibitors achieved marrow responses (CRc) to the second generation FLT3 inhibitors quizartinib(23-25) and gilteritinib(26), with 20-30% bridged to allogeneic stem cell transplant. Of note, recent FDA approval of midostaurin in combination with 7+3 induction chemotherapy in newly diagnosed FLT3-mutant AML signifies that essentially all relapsed FLT3-mutated AML patient will likely been exposed to at least one FLT3 targeting TKI. In this setting, the marrow response (CRc) rates with second generation FLT3 inhibitors such as crenolanib, gilteritinib and quizartinib have been reported to be lower than in prior FLT3 TKI naïve patients and are in the range of 20-25% (26, 48, 49) and Daiichi Sankyo unpublished communication).

Although response rates are high, the responses to single agent second generation *FLT3* inhibitors are almost invariably transient, maintained for 14-17 weeks, except among patients who undergo transplantation, due to the emergence of resistance(27, 28). The causes of resistance include the acquisition of point mutations in the *FLT3* KD (in 30-40% of resistant cases) and non-mutational mechanisms of resistance (in 50-60% of resistant cases) including up-regulation of compensatory pathways including the activation of anti-apoptotic proteins *BCL2*, *MCL1* and *BCL-x(L)*, *PI3K/Akt/mTOR*, *FOXO3A*, *SYK*, *RAS* and *STAT5/PIM* pathways, up-regulation of the *FLT3* ligand or receptor, mutations in other kinases (e.g. *CBL*), and tumor microenvironment mediated resistance(31).

[figure not shown]
MCL-1 was reported as an essential effector of *FLT3-ITD*-mediated drug resistance (50) and a number of *FLT3* inhibitors down-regulate *MCL1* thereby reducing the propensity to resistance to *BCL2* inhibitors. Combination of ABT-737 and *FLT3* inhibitors was synergistic in *FLT3-ITD*-mutated AML(51).

Furthermore, our recent data shows that *FLT3-ITD* activation/mutations may play a major role in primary and secondary resistance to ABT-199 (Popovic R, [name] et al, manuscript accepted to *American Journal of Hematology* May 2018). A phase 2 trial evaluated the efficacy and safety of venetoclax monotherapy in 32 patients with

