9.1.4 Follow-Up at Treatment Discontinuation or Early Withdrawal

Patients who discontinue treatment for any reason should complete end-of-treatment procedures when possible. End of treatment procedures will include a physical examination, CBC with differential and platelets and a limited chemistry profile (total bilirubin, serum creatinine, SGPT or SGOT). A bone marrow aspiration may be recommended only if non-response or progressive disease cannot be unequivocally diagnosed from peripheral blood. Although treatment will be discontinued at that time, all patients who do not withdraw consent for follow-up, die, or become lost to follow-up, will remain on study for follow-up evaluations. Subject will be followed for toxicity for at least 30 days after the last protocol treatment. The 30-day (+/-7 days) follow-up visit will be scheduled as a clinic visits for clinical evaluation and physical examinations. If the patient cannot make it to the MDACC clinic for this visit, the required follow up treatment procedures may be done with a local physician and the records forwarded to MDACC. The research nurse will contact the patient by telephone and get a verbal assessment of the patient's condition. The phone conversation will then be documented in the patient's charts.

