11.3 Statistical Analysis Plan

All patients who receive any dose of the study agent will be included in the analysis for efficacy and safety. We will follow standard reporting guidelines for adverse events, and summarize safety data by category, severity and frequency. For the primary efficacy analysis, we will estimate the CRc rate for the combination treatment, along with the 95% credible interval. Patients who drop out of the study before completing all the cycles will be treated as “failures” for the primary analysis.

Patients’ demographic and clinical characteristics will be summarized using descriptive statistics. Specifically, categorical covariates will be summarized by frequencies and percentages and their associations with responses will be assessed using Fisher’s exact test or its generalization. Continuous covariates will be summarized by means, standard deviations, medians and ranges, and the difference between responses groups will be assessed using the Wilcoxon rank sum test. Paired t-tests or Wilcoxon signed-rank tests will be used to determine the immunological and molecular changes in the peripheral blood and bone marrow from baseline to the time of response, and to the time of disease progression.

We will estimate the rates of partial response and bone marrow blast reduction $\geq 50\%$ within 3 months, along with 95% confidence intervals. For each subject, duration of response (DOR), event-free survival time and overall survival time will be calculated. DOR is defined as the time period from the first documentation of CRc to disease

recurrence, disease progression, or death whichever occurs first. Event-free survival time is defined as the time period from the date of treatment initiation to the date of documented treatment failure, relapses from CRc, or death from any cause, whichever occurs first. The observed DOR/EFS will be censored at the last follow-up if the patient is alive and no events observed. The overall survival time is defined as the time duration from treatment start till death or last follow-up if the patient is alive. The distributions of time-to-event endpoints including OS and DOR will be estimated using the Kaplan-Meier method. Comparisons of time-to-event endpoints by important covariate subgroups will be made using the log-rank tests. Progressive disease will be determined using ELN (2017) recommendations and is defined as any one or more of the following:

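### The protocol gives conflicting rules for scoring the primary CRc in patients who stop treatment before three cycles, and none closes the response window at HSCT or new anti-leukemic therapy

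*Combined protocol and SAP*

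**What the plan says.** Five sections bear on how a patient who stops early is scored.

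- **Section 1.1** sets the phase II objective as CRc "within 3 months of treatment initiation in FLT3-ITD mutated patients with relapsed/refractory AML". This is a calendar window.
- **Section 8.8** takes the best response over the first three cycles, "or at time off study, for those patients discontinuing treatment before the completion of 3 cycles of therapy". Its last sentence defines a second measure differently: "Best response will also be evaluated for the full treatment period using all assessments up to and including treatment discontinuation".
- **Section 9.1.4** says that after treatment stops, "all patients who do not withdraw consent for follow-up, die, or become lost to follow-up, will remain on study for follow-up evaluations". Section 9.1.1 likewise lets a patient leave treatment but stay in the study.
- **Section 11.2** defines the primary endpoint as CRc at any time in the first three cycles of therapy, and in the same paragraph says CRc is monitored with a 3-month window.
- **Section 11.3** analyses everyone who receives any dose. It adds: "Patients who drop out of the study before completing all the cycles will be treated as" failures in the primary analysis.

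No section says what happens to response scoring once a patient starts another anti-leukemic therapy or goes to HSCT. Bridging to HSCT is itself a secondary objective (section 1.2).

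**The concern.** The CRc count feeds both the primary estimate and the Table 4 futility boundary. Both judge the combination against a fixed 25% for quizartinib alone, with no concurrent control to absorb a scoring error. With 20 patients, each reclassified patient moves the observed CRc by 1/20, or 5 percentage points.

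The ambiguity can act in either direction:

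- If response stays open until the patient leaves the study, a remission brought about by transplant or another salvage regimen can be credited to the combination. That can only raise the count and weaken futility stopping.
- If stopping treatment early makes a patient a failure, a genuine on-treatment CRc followed by HSCT is lost. That can only lower the count.

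Two analysts working from the same data could report different primary results, and could disagree on whether accrual should stop.

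**Working it through.** **1. The passages applied to two illustrative patients**

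Patient A has a partial remission after cycle 1, stops treatment, goes to HSCT or another regimen, and a marrow in month 3 shows CR. Patient B reaches CRc after cycle 1, stops treatment and goes to HSCT.

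| Rule | Patient A | Patient B |
|---|---|---|
| 8.8 with 9.1.4 and 1.1, literal | CRc | CRc |
| 8.8, if off study means off treatment | not CRc | CRc |
| 11.2, first three cycles of therapy | not CRc, if cycles end with treatment | CRc |
| 11.3, if dropping out means stopping treatment | failure | failure |
| 11.3, if dropping out means leaving the study | rule does not apply | rule does not apply |

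The strict reading of 11.3 is severe. Section 5.3.1 plans up to 24 cycles, so failing everyone who stops before all the cycles would reach well past the three-cycle endpoint.

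**2. The plan's own figures**

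Inputs from section 11.2: prior Beta(0.5, 1.5); stop if Pr(CRc > 0.25 + 0.25 = 0.50 | data) < 0.025; looks at 10 and 15 patients. With x responders in n, the posterior is Beta(0.5 + x, 1.5 + n − x).

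- 2/10: 0.0149, stop. 3/10: 0.064, continue.
- 4/15: 0.0210, stop. 5/15: 0.0656, continue.

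This reproduces Table 4. Exact calculation with independent response and toxicity reproduces all 25 cells of Table 6 to within 0.0001 (for example 0.1605 at CRc 50% and toxicity 30%). No design figure is in dispute.

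**3. Sensitivity of the futility rule**

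For a counted CRc of p, the futility-only stopping probability is

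P(X10 ≤ 2) + P(X10 = 3)·P(X5 ≤ 1) + P(X10 = 4)·P(X5 = 0),

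where X10 and X5 are binomial counts in the first 10 and the next 5 patients.

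- p = 25%: 0.5256 + 0.2503 × 0.6328 + 0.1460 × 0.2373 = 0.5256 + 0.1584 + 0.0346 = 0.7186
- p = 30%: 0.3828 + 0.2668 × 0.5282 + 0.2001 × 0.1681 = 0.3828 + 0.1409 + 0.0336 = 0.5574 (rounded terms sum to 0.5573)
- p = 35%: 0.2616 + 0.2522 × 0.4284 + 0.2377 × 0.1160 = 0.2616 + 0.1081 + 0.0276 = 0.3972 (rounded terms sum to 0.3973)

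The first and third agree with Table 6 at 10% toxicity (0.7188 and 0.3976), where toxicity stopping adds almost nothing.

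If the true on-treatment CRc is 25% and an average of one patient in 20 is misattributed, the counted rate is 30%; with two in 20 it is 35%. These numbers are assumptions; the documents give none.

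**4. At a boundary**

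One added patient of type A turns 2/10 into 3/10, so accrual continues. One lost patient of type B turns 3/10 into 2/10, so accrual stops.

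**The case against.** A reader might infer that patient A simply is a CRc under the plan and that the reported rate is therefore biased upward. The documents do not support that, for these reasons:

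- Section 11.2 defines the endpoint by cycles of therapy, and a patient on salvage or after transplant is not in a protocol cycle.
- Section 3.4 uses coming off study to mean leaving protocol therapy. Read that way, 8.8 agrees with 11.2.
- Section 4.1, criterion 8, bars other anti-leukemic agents during the study, with listed exceptions.
- No response marrow is scheduled after treatment ends. The end-of-treatment marrow in 9.1.4 is conditional, and later survival follow-up (7.2.13) may be by telephone. Section 8.0 also speaks of a confirmed remission rate.
- One reading of 11.3 fails patient A outright.

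These points make misattribution less likely and rule out calling it the plan's settled rule. They do not remove the conflict. Section 8.8 is the only text written specifically for early stoppers, and within one paragraph it uses two different end points. The 3-month window limits when a remission is seen, not what caused it. The ban in 4.1 does not mention HSCT and is not a scoring rule. Unscheduled marrows are not excluded. The reading of 11.3 that closes the gap does so by discarding patient B.

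Nor can the size of the effect be taken from section 2.4, which reports second-generation FLT3 inhibitor results "with 20-30% bridged to allogeneic stem cell transplant". That figure concerns patients not previously exposed to FLT3 inhibitors, and many of those bridged may already have been in CRc. It shows that transplant is expected, not how many non-responders would later be counted.

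**Conclusion.** The concern holds as a conflict among sections 1.1, 8.8, 9.1.4, 11.2 and 11.3 on scoring early stoppers, together with the absence of any cut-off at HSCT or new therapy. It does not hold as a finding that post-transplant remissions are counted, or that the CRc rate is inflated: the literal reading of 8.8 can raise the count, the strict reading of 11.3 can lower it, and the number of affected patients is unknown.

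The calculations show only that the rule is sensitive. One patient can cross the boundary at the first look. A counted rate 5 points above a true 25% reduces futility stopping from 0.719 to 0.557, and 10 points above reduces it to 0.397. These figures assume one or two misattributed patients per 20 on average, independent outcomes and the Table 4 looks. The wording should be repaired before the primary analysis and before any Table 4 look, because it governs the primary count and costs little to settle.

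**What to change.** In section 8.8, replace the off-study wording with a single rule: best response documented within the first three cycles/3 months, and up to the earlier of (a) treatment discontinuation, including the end-of-treatment assessment, and (b) the start of any non-protocol anti-leukemic therapy or HSCT conditioning. State which limit binds when three cycles and 3 months differ.

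Align sections 1.1, 11.2 and 11.3 to that rule, and say that it also governs the Table 4 counts. A CRc documented before the cut-off is kept, even if the patient then stops treatment or goes to HSCT. Early stoppers without one are non-responders and stay in the denominator. In 11.3, replace the drop-out sentence with this statement.

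Cost: protocol and SAP wording, plus recording the start date of the next therapy or HSCT conditioning; HSCT timing is already needed for the section 1.2 objective. The reported CRc may be slightly lower than under the literal reading of 8.8. Boundaries, sample size and Table 6 are unchanged.

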9.1 Discontinuation Criteria for Individual Patients

9.1.1 Patient Withdrawal

Patients may voluntarily withdraw consent to participate in the clinical study at any time and without giving any reason. Their withdrawal will not jeopardize their relationship with their healthcare providers or affect their future care. Patients may also choose to withdraw from study treatment, but agree to remain in the study for follow-up procedures.

9.1.2 Investigator Discontinuation of Patient

The investigator may exercise medical judgment to discontinue study treatment if clinically significant changes in clinical status or laboratory values are noted.

9.1.3 Criteria for Protocol-Defined Required Discontinuation of Treatment

The protocol requires discontinuation of study treatment for the following reasons:

1. Patient requests discontinuation.
2. Unacceptable toxicity that in the opinion of the investigator makes it unsafe to continue therapy.
3. Clinically significant progressive disease.
4. Investigator discretion.

9.1.4 Follow-Up at Treatment Discontinuation or Early Withdrawal

Patients who discontinue treatment for any reason should complete end-of-treatment procedures when possible. End of treatment procedures will include a physical examination, CBC with differential and platelets and a limited chemistry profile (total bilirubin, serum creatinine, SGPT or SGOT). A bone marrow aspiration may be recommended only if non-response or progressive disease cannot be unequivocally diagnosed from peripheral blood. Although treatment will be discontinued at that time, all patients who do not withdraw consent for follow-up, die, or become lost to follow-up, will remain on study for follow-up evaluations. Subject will be followed for toxicity for at least 30 days after the last protocol treatment. The 30-day (+/-7 days) follow-up visit will be scheduled as a clinic visits for clinical evaluation and physical examinations. If the patient cannot make it to the MDACC clinic for this visit, the required follow up treatment procedures may be done with a local physician and the records forwarded to MDACC. The research nurse will contact the patient by telephone and get a verbal assessment of the patient's condition. The phone conversation will then be documented in the patient's charts.

9.2 Study Stopping Rules

The principal investigator, the MDACC IND office (Sponsor) and the supporting companies (Daiichi-Sankyo and Abbvie) have the right to terminate this clinical study at any time. The principal investigator and MDACC IND office, as appropriate, will be involved in any decisions regarding terminating the study, temporarily suspending enrollment, or stopping ongoing treatment with study treatment.

Reasons for terminating the clinical study or a study site's participation include, but are not limited to, the following:

- The incidence or severity of an adverse reaction related to treatment in this study or other studies indicates a potential health hazard to patients
- Data recording is significantly inaccurate or incomplete
- Study site personnel are noncompliant with study procedures
- Pattern of noncompliance is observed

9.3 Protocol Violations and Deviations

Protocol violations are defined as significant departures from protocol-required processes or procedures that affect patient safety or benefit potential, or confound assessments of safety or clinical activity. A protocol deviation is a departure from the protocol that does not meet the above criteria. Protocol violations or deviations may be grouped into the following classes:

- Enrollment criteria

- Study activities (missed evaluations or visits) except for those allowed per protocol
- Noncompliance with dose or schedule, including dose calculation, administration, interruption, reduction, or delay; or discontinuation criteria
- Investigational product handling, including storage and accountability
- Informed consent and ethical issues

10.0 ADVERSE EVENT REPORTING

10.1 Adverse event is any untoward medical occurrence that may present during treatment with a pharmaceutical product but which does not necessarily have a causal relationship with this treatment.

Adverse drug reaction is a response to a drug which is noxious and unintended and which occurs at doses normally used in man for prophylaxis, diagnosis, or therapy of disease or for the modification of physiologic function.

Assessing causal connections between agents and disease is fundamental to the understanding of adverse drug reactions. In general, a drug may be considered a contributory cause of an adverse event if, had the drug not been administered, 1) the event would not have happened at all, 2) the event would have occurred later than it actually did, or 3) the event would have been less severe.

The Investigator or physician designee is responsible for providing source documentation and assigning attribution for all AEs.

10.2 Adverse Events (AEs) will be evaluated against the most current version of the venetoclax and quizartinib IBs for expectedness. Adverse Events (AEs) will be evaluated according to the latest CTCAE version 5.0 and documented in medical record. AEs will be recorded in the Case Report Form (CRF). The Leukemia-specific Adverse Event Recording and Reporting Guidelines (Appendix G) will be used for reporting.

10.3 **Abnormal hematologic values will not be recorded on the case report form. For abnormal chemical values, the apogee or nadir (whichever is appropriate) will be reported per course on the case report form, unless the event is considered a DLT as listed in section 3.4.**

10.4 **Serious Adverse Event Reporting (SAE)**

An adverse event (AE) or suspected adverse event is considered “serious” if, in the view of either the investigator or the sponsor, it results in any of the following outcomes:

- Death
- A life-threatening adverse drug experience – any adverse experience that places the patient, in the view of the initial reporter, at immediate risk of death from the adverse experience as it occurred. It does not include an adverse experience that might have caused death if it had occurred in a more severe form.

- Inpatient hospitalization or prolongation of existing hospitalization, not to include planned hospitalization for ramp-up portion of the therapy
- A persistent or significant incapacity or substantial disruption of the ability to conduct normal life functions.
- A congenital anomaly/birth defect.

Important medical events that may not result in death, be life-threatening, or require hospitalization may be considered a serious adverse drug experience when, based upon appropriate medical judgment, they may jeopardize the patient or subject and may require medical or surgical intervention to prevent one of the outcomes listed in this definition. Examples of such medical events include allergic bronchospasm requiring intensive treatment in an emergency room or at home, blood dyscrasias or convulsions that do not result in inpatient hospitalization, or the development of drug dependency or drug abuse (21 CFR 312.32).

- Important medical events as defined above, may also be considered serious adverse events. Any important medical event can and should be reported as an SAE if deemed appropriate by the Principal Investigator or the IND Sponsor, IND Office.
- All events occurring during the conduct of a protocol that meet the definition of a SAE must be reported to the IRB in accordance with the timeframes and procedures outlined in “University of Texas M. D. Anderson Cancer Center Institutional Review Board Policy for Investigators on Reporting Unanticipated Adverse Events for Drugs and Devices.” Unless stated otherwise in the protocol, all SAEs, expected or unexpected, must be reported to the IND Office, regardless of attribution (within 5 working days of knowledge of the event).
- **All life-threatening or fatal events**, that are unexpected, and related to the study drug, must have a written report submitted within **24 hours** (next working day) of knowledge of the event to the Safety Project Manager in the IND Office.
- Unless otherwise noted, the electronic SAE application (eSAE) will be utilized for safety reporting to the IND Office and MDACC IRB.
- Serious adverse events will be captured from the time of the first protocol-specific intervention, until 30 days after the last dose of drug, unless the participant withdraws consent. Serious adverse events must be followed until clinical recovery is complete and laboratory tests have returned to baseline, progression of the event has stabilized, or there has been acceptable resolution of the event.
- Additionally, any serious adverse events that occur after the 30-day time period that is related to the study treatment must be reported to

the IND Office, Abbvie Inc and Daiichi-Sankyo. This may include the development of a secondary malignancy.

- All cases of venetoclax or quizartinib overdose (defined as accidental or intentional ingestion of any dose of the product that is considered excessive and medically important) must be reported as an SAE to the Sponsor (MDACC IND office) and to the supporting company on the SAE Form.
- Pregnancy alone is not considered an AE. However, if a patient becomes pregnant or causes a pregnancy during treatment or within 6 months of ending treatment, even if the subject is withdrawn from the study, the pregnancy must be reported immediately to the sponsor (MDACC IND office) on the MD Anderson SAE Form and to the supporting company within 1 days of the Investigator's knowledge of the pregnancy. The investigator should abide by necessary regulation for medical release from a female partner of a male subject prior to obtaining follow up. The investigator will follow the pregnancy to term or termination, will collect data on both the maternal and fetal outcome and will report all outcomes as a follow-up report to the initial pregnancy notification to the supporting company, Daiichi-Sankyo and Abbvie Inc. Notwithstanding, all pregnancy outcomes that meet the regulatory definition of serious (i.e. spontaneous abortion, neonatal death, congenital anomaly in an aborted fetus or neonate) will be reported on the MD Anderson SAE Form to the sponsor (MDACC IND office) and the supporting companies within 24 hours of Investigator knowledge of the outcome.

10.4.1 Adverse Events of Special interest (AESI):

- a. **QTc Prolongation, TdP, and Other Ventricular Arrhythmias** Subjects who experience >480 msec QTcF prolongation and undergo dose interruption and/or reduction must be monitored closely with ECGs, performed twice weekly for the first week of the QTcF prolongation and then weekly thereafter until the QTcF prolongation is resolved, as described in Section 5.2.2.(dose modification section).
 - a. QTcF prolongation \geq Grade 3, either serious or non-serious and whether or not causally related, must be recorded as AE or SAE in the [Electronic Data Capture (EDC)], with the Investigator's assessment of seriousness, causality, and a detailed narrative.
 - Electrolytes (potassium, calcium, and magnesium) should be checked and supplementation given to correct any values outside the normal range;
 - Concomitant medications should be reviewed to identify and, if appropriate, discontinue any medication with known QT prolonging effects (section 5.5.2);
 - Subjects who experience >480 msec QTcF prolongation and undergo dose interruption and/or reduction must be

monitored closely with ECGs, performed twice weekly for the first week of the QTcF prolongation and then weekly thereafter until the QTcF prolongation is resolved.**b.**

.Combined Elevations of ATs and Bili

Combined elevations of aminotransferases and bilirubin, either serious or non-serious and whether or not causally related, meeting the laboratory criteria of a potential Hy's Law case [ALT or AST $\geq 3 \times$ ULN with simultaneous TBL $\geq 2 \times$ ULN] should always be recorded as an AE or SAE within 24 hours of awareness, with the Investigator's assessment of seriousness, causality, and a detailed narrative. Subjects will be monitored as described below:

Evaluation may include the following depending on the clinical situation:

- Medical history and physical exam, including focus on medications and substances used: alcohol, acetaminophen, azole antifungals, change in medication dosages, new medications added, over the counter medication use and recreational drug use. Check for change in diet or use of dietary supplements;
- Abdominal ultrasound;
- Hepatitis A, B, C, and E screening (anti-hepatitis A virus immunoglobulin M, hepatitis B surface antigen, anti-hepatitis C virus plus viral titer, and evaluation for Hepatitis E), antinuclear antibody and anti-Smith antibody, cytomegalovirus, Epstein Barr virus;
- Additional evaluations as deemed appropriate by the Investigator to exclude other causes of liver enzyme and bilirubin elevations;
- All laboratory results, including local laboratory reference ranges are to be recorded.

